4.1.2 Exclusion Criteria

Participants meeting any of the following criteria will be excluded from the study:

- 1. Participant is female and has a positive serum pregnancy test result at Screening or plans to become pregnant during the study.
- 2. Participant is female and is breastfeeding or plans to breastfeed from study vaccination to 3 months after study vaccination.
- 3. Has any clinically significant abnormal biochemistry or hematology finding (defined as ≥Grade 1; Section 6.1.2) at Screening. Note: Older adults (aged ≥65 years) with Grade 1 laboratory abnormalities which have been stable for at least 6 months prior to enrollment may be included in the study.
- 4. Has any medical disease or condition that, in the opinion of the investigator, precludes study participation. This includes any acute, subacute, intermittent, or chronic medical disease or condition that would place the participant at an unacceptable risk of injury, render the participant unable to meet the requirements of the protocol, or may interfere with the evaluation of responses or the participant's successful completion of the trial.
- 5. Any confirmed or suspected immunosuppressive or immunodeficient condition resulting from disease (eg, malignancy) or immunosuppressive/cytotoxic therapy (eg, medications used during cancer chemotherapy, organ transplantation, or to treat autoimmune disorders).
- 6. History of myocarditis, pericarditis, or idiopathic cardiomyopathy, or presence of any medical condition that increases risk of myocarditis or pericarditis, including cocaine abuse, cardiomyopathy, endomyocardial fibrosis, hypereosinophilic syndrome, hypersensitivity myocarditis, eosinophilic granulomatosis with polyangiitis, persistent myocardial viral infection (eg, due to enterovirus or adenovirus), and celiac disease.
- 7. [Edited and moved to exclusion criterion 24i]
- 8. Has an acute febrile illness with a temperature ≥38.0°C or ≥100.4°F observed by the participant or at the study site within 72 hours prior to study vaccination. Participants with suspected COVID-19 symptoms (Section 6.6) should be excluded and referred for medical care.

- 9. Has a prior confirmed diagnosis of chronic hepatitis B, hepatitis C, or HIV 1/2 infection or evidence of active infection at Screening.
- 10. Has participated or plans to participate in another investigational study involving any investigational drug or device within 60 days or 5 half-lives, whichever is longer, before study vaccination and throughout the end of the study.
- 11. Has previously participated in another investigational vaccine study with investigational vaccine administered within 6 months of study vaccination.
- 12. Has received or plans to receive any licensed vaccine within 4 weeks before or after study vaccination. Inactivated vaccines for influenza are permitted during the study if they are administered at least 14 days before or after study vaccination.
- 13. Is planning to receive an authorized or licensed COVID-19 booster vaccination for the duration of the study (for adults who are not covered by local recommendations to receive booster per current standard of care) OR Is planning to receive an authorized or licensed COVID-19 booster vaccination on or before Day 29 of the study (for adults covered by local recommendations to receive booster).
- 14. Has received or plans to receive immunoglobulins or any blood or blood products within 90 days before study vaccination and throughout the study.
- 15. Has a history of hypersensitivity or severe allergic reaction, including anaphylaxis, generalized urticaria, angioedema, and other significant reactions to any previous vaccine or any component of the IP.
- 16. Has a history of hypersensitivity or severe allergic reaction (including anaphylaxis, generalized urticaria, angioedema, and other significant reactions) to beta lactam antibiotics.
- 17. Reports chronic use (more than 14 continuous days) of any medication that may be associated with changes in immune function including, but not limited to, systemic corticosteroids exceeding 10 mg/day of prednisone equivalent, allergy injections, immunoglobulins, interferons, immunomodulators, cytotoxic drugs, or other similar or toxic drugs within 6 months of study vaccination. Note: The use of low-dose topical, ophthalmic, inhaled, and intranasal steroid preparations is permitted.

- 18. Has a bleeding disorder (eg, factor deficiency, coagulopathy, or platelet disorder), or prior history of significant bleeding or bruising after IM injections or venipuncture.
- 19. Has a history of alcohol abuse or other recreational drug use (excluding cannabis) within 6 months before study vaccination.
- 20. Has any abnormal skin condition or permanent body art (eg, tattoo) that would interfere with the ability to observe local reactions at the study vaccination injection site.
- 21. Has had known close contact with anyone who had a confirmed SARS-CoV-2 infection within 14 days before study vaccination.
- 22. Participant is an employee or family member of the investigator or study site personnel.
- 23. Has any self-reported or medically documented significant medical or psychiatric condition. Significant medical conditions include, but are not limited to, the following:
 - a. Moderate or severe respiratory disease (eg, chronic obstructive pulmonary disease, asthma)
 - b. Uncontrolled hypertension, defined as an average systolic blood pressure ≥140 mmHg for participants ≤60 years old, and ≥150 mmHg for participants >60 years old, or a diastolic blood pressure ≥90 mmHg for any age
 - c. Significant cardiovascular disease (eg, congestive heart failure, cardiomyopathy, ischemic heart disease) or history of myocarditis or pericarditis
 - d. Neurological or neurodevelopmental conditions (eg, Down's syndrome, dementia, chronic migraine not controlled by medication, epilepsy, stroke, or seizure in the last 3 years, encephalopathy, focal neurologic deficits, Guillain-Barré syndrome, encephalomyelitis, or transverse myelitis)
 - e. Ongoing malignancy or recent diagnosis of malignancy in the last 5 years (excluding basal cell and squamous cell carcinoma of the skin)
 - f. Tuberculosis or nontuberculosis mycobacterial infection
 - g. Autoimmune disease, including hypothyroidism without a defined nonautoimmune cause

- h. Immunodeficiency of any cause, including from solid organ transplant, blood or bone marrow transplant, use of corticosteroids, or use of other immune-weakening medicines
- i. Type 1 or 2 diabetes mellitus regardless of disease control
- 24. Has any of the following self-reported or medically documented risk factors for severe COVID-19:
 - a. Cancer
 - b. Chronic kidney disease
 - c. Sickle cell disease
 - d. Cerebrovascular disease
 - e. Cystic fibrosis
 - f. Chronic liver disease
 - g. Pulmonary fibrosis
 - h. Thalassemia
 - i. Smoking or other inhaled substance use, including tobacco, cannabis, or nicotine vapors, with an average of ≥5 cigarettes a day or equivalent (currently or within 1 year of Screening).
- 25. Has a history of documented SARS-CoV-2 infection or COVID-19 within 6 months before Screening.

4.1.3 Screen Failures

Screen failures are defined as participants who consent to participate in the clinical study but are not subsequently randomly assigned to study intervention. A minimal set of screen failure information is required to ensure transparent reporting of screen failure participants. Minimal information includes demography, screen failure details, eligibility criteria, and any SAE.

Individuals who do not meet the criteria for participation in this study (screen failure) may be rescreened under a different participant number. A maximum of one rescreen is allowed.

Participants who are rescreened are required to sign a new ICF prior to undergoing rescreening assessments.

4.2 Discontinuation From Study Vaccine and/or Withdrawal From the Study

As this is a single dose booster vaccination study, discontinuation from IP does not apply; however, participants may withdraw from the study at any time and for any reason without prejudice to their future medical care by the investigator or at the study site. Every effort should be made to keep participants in the study for follow-up evaluations. The reasons for participants withdrawing from the study will be recorded.

Participants will be informed of any authorized or licensed booster vaccines available for COVID-19 during the study to support an informed choice for whether to continue or discontinue participation in the study.

A participant may withdraw or be withdrawn from the study for any of the following reasons:

- 1. The participant does not meet the protocol inclusion or exclusion criteria.
- 2. The participant is noncompliant with the protocol.
- 3. The participant has a serious or intolerable AE(s) that, in the investigator's opinion, requires withdrawal from the study.
- 4. The participant has safety laboratory results that reveal clinically significant hematological or biochemical changes from the baseline values, per investigator judgment.
- 5. The participant has symptoms or an intercurrent illness not consistent with the protocol requirements or that justify withdrawal. Note: Such events should also be reported as AEs.
- 6. The participant is lost to follow-up.
- 7. Other reasons (eg, pregnancy, development of contraindications of use of the IP).
- 8. The participant withdraws consent, or the investigator or sponsor decides to discontinue their participation in the study.

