• Participants with medically documented risk factors for severe COVID-19 disease will be excluded from the study and the occurrence of 2 cases of severe COVID-19 disease will trigger the hold of the whole Phase 1 study.

Participants will receive close medical supervision and medical assessments (eg, laboratory testing) during the study.

The investigational CV2CoV vaccine is currently in an early stage of clinical development and vaccine efficacy, immunogenicity, and safety have not yet been demonstrated in humans. Considering the risk mitigation strategies, measures taken, and planned to be taken to minimize risk to participants in this Phase 1 clinical trial, the potential risks associated with the investigational vaccines are considered acceptable.

2 Study Objectives and Endpoints

The study objectives and endpoints are described in Table 2-1.

Table 2-1 Study Objectives and Endpoints

Objectives	Endpoints				
Primary – Safety					
To evaluate the safety and reactogenicity of CV2CoV at each dose level in SARS-CoV-2 seropositive healthy adult participants after booster vaccination	Percentage of participants with MAAEs, SAEs, and AESIs from study vaccination through the end of the study (approximately 180 days after the study vaccine administration), each summarized separately				
	Percentage of participants with each solicited local and systemic AE within the 7-day postvaccination period (Days 1 to 7)				
	Percentage of participants with unsolicited AEs up to 28 days after study vaccination, including clinically relevant abnormal laboratory findings				
Secondary – Immunogenicity					
To explore the dose response and effect of CV2CoV at each dose level on neutralizing Ab titers against pseudovirus bearing spike protein from SARS-CoV-2 WT in SARS-CoV-2	GMTs of neutralizing Ab titers against pseudovirus bearing spike protein from either SARS-CoV-2 WT at each collection time point (Days 1, 8, 15, 29, 85, and 180)				
seropositive healthy adult participants after booster vaccination	• Percentage of participants with seroresponse (≥4-fold rise from baseline) at Day 29 after the booster dose				
	GMI from baseline of neutralizing Ab titers against pseudovirus bearing spike protein from SARS-CoV-2 WT at each collection time point (Days 8, 15, 29, 85, and 180)				

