4.2.1 Discontinuation From Study Vaccine

Only a single dose booster vaccination will be administered to each participant; thus, discontinuation from study vaccine is not applicable.

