5.8.2 Allowed Concomitant Therapy

Any concomitant medication deemed necessary for the welfare of the participant during the study may be given at the discretion of the investigator. However, it is the responsibility of the investigator to ensure that details regarding the medication are recorded in full in the eCRF.

The following concomitant therapies are allowed during the study:

- Acetaminophen/paracetamol
- Contraception, as described in Appendix 13.2
- Low-dose topical, ophthalmic, inhaled, and intranasal steroid preparations
- Local intra-articular steroids that are expected to remain localized in the joint space in which they are administered
- Inactivated influenza vaccines are allowed if received at least 14 days before or after study vaccination. Note: If other nonstudy vaccines are received during the study, participants may continue to complete the remaining study assessments. Any impact on the immunogenicity data will be addressed in the data analysis.

 Participants may take concomitant medications for management of medically stable chronic conditions as long as the medication and medical conditions are not exclusionary (Section 4.1.2)

Participants will be allowed to receive a booster dose of a licensed or authorized (conditional regulatory approvals, including emergency use authorizations are acceptable) COVID-19 vaccine, per national recommendations, if received after the Day 29 visit.

No concomitant medications will be provided by the sponsor or PPD.

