6.1.1.2 Eliciting and Documenting Adverse Events

Adverse events will be reported throughout the study. Nonserious AEs will be reported from the time of the administration of IP until 28 days after the administration of IP; SAEs will be reported from the time the participant signs the ICF until exit from the study.

If the investigator learns of any SAE, including a death, at any time after a participant has been discharged from the study, and he/she considers the event to be reasonably related to the IP, the investigator must notify PPD Pharmacovigilance within 24 hours of learning of the event (Section 6.1.1.3.1).

At every study visit, participants will be asked a standard nonleading question to elicit any medically related changes in their well-being.

In addition to participant observations, AEs identified from any study data (eg, laboratory values, physical examination findings) or identified from review of other documents (eg, participant eDiaries) that are relevant to participant safety will be documented on the AE page in the eCRF.

As described in Section 6.1.1.1.1, participant eDiaries will be used to collect solicited AEs.

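### Section 4.2 permits study withdrawal after the only dose, and nothing keeps withdrawn vaccinated participants under scheduled collection of new SAEs, MAAEs and AESIs to Day 180

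*Protocol*

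**What the plan says.** Protocol Section 4.2 opens with "As this is a single dose booster vaccination study, discontinuation from IP does not apply", and Section 4.2.1 repeats this: "Only a single dose booster vaccination will be administered to each participant; thus, discontinuation from study vaccine is not applicable". Section 4.2 then introduces its list with "A participant may withdraw or be withdrawn from the study for any of the following reasons". The list includes "The participant has a serious or intolerable AE(s) that, in the investigator's opinion, requires withdrawal from the study" and "The participant has safety laboratory results that reveal clinically significant hematological or biochemical changes from the baseline values, per investigator judgment". It also includes intercurrent illness, noncompliance, failure to meet eligibility criteria, pregnancy or a contraindication to the product, and an investigator or sponsor decision. No reason is limited to the period before vaccination. The same section asks sites to make every effort at retention.

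On withdrawal, Section 4.2.2 calls for the early termination procedures. No later scheduled contact is stated.

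Table 2-1 makes this a primary endpoint: "Percentage of participants with MAAEs, SAEs, and AESIs from study vaccination through the end of the study", that is, to about Day 180. Section 6.1.1.2 says "SAEs will be reported from the time the participant signs the ICF until exit from the study". After discharge, it requires a report only of an SAE that the investigator learns of and considers related. Footnote m of Table 13-1 ties MAAE and AESI collection to the duration of the study, and SAP Sections 9.1.6 to 9.1.8 end the reporting of AESIs, SAEs and MAAEs at study exit. SAP Section 9.1 bases adverse event percentages on the Safety Set in each dose group.

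**The concern.** A withdrawal list of this kind usually serves partly to stop further dosing. Here no dose follows Day 1, so withdrawing a vaccinated participant stops procedures and observation. The procedures may be worth stopping. The observation is the primary endpoint.

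Two other places show that withdrawal after vaccination is expected. Holding rule 1c in Table 5-2 is triggered by a withdrawal following a Grade 3 AE, whether the investigator or the participant asks for it. Section 4.2.4 says that participants who leave for reasons connected to the vaccine should in general not be replaced, so the lost observation is generally not made up.

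A participant who leaves early counts as not having any category of event that had not been recorded by exit. If the reason for leaving is itself a safety finding, the loss may be informative. The late safety percentages for that dose group would then tend to be too low.

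**Working it through.** **Inputs.** 30 participants per dose group (Protocol 3.1 and 7.2). Collection window Day 1 to Day 180 (Table 2-1; SAP Section 4). Denominator: the whole Safety Set of the dose group (SAP 9.1). Protocol 7.6 leaves missing safety data to the SAP. The SAP imputes incomplete adverse event dates but gives no adjustment for shortened follow-up. Neither document gives a withdrawal rate for safety. The only attrition figure is a 10% unevaluable rate for immunogenicity (Protocol 7.2). I assume k = 1, 2 or 3 of 30 withdrawn; the top of that range equals 10% of 30.

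**The plan's own figure.** The probability of at least one event is 1 − (1 − p)^n. With n = 30 it is 1 − 0.95^30 = 78.5% and 1 − 0.90^30 = 95.8%. Both match Section 7.2, and both suppose that all 30 are observed.

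**Observation lost.** For an assumed exit at Day 29, 180 − 29 = 151 days are lost, and 151/180 = 84%.

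**Effect on a percentage.** This concerns one event category not yet recorded in the k participants at exit.

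- Largest possible shift: k/30, if every withdrawn participant has an unseen event.
- Exact two-sided 95% upper limit with no events among n fully observed: 1 − 0.025^(1/n). For n = 30 this is 11.6%.
- Expected observed percentage, assuming 5% late risk in those retained: (30 − k) × 0.05/30.
- Expected percentage with full follow-up, assuming late risk r in those withdrawn: [(30 − k) × 0.05 + k × r]/30, with r from 5% to 40%.

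| k | Largest shift (points) | Upper limit, 0 of 30 − k | P(at least 1), p = 5% | P(at least 1), p = 10% | Expected observed | Expected, full follow-up |
|---|---|---|---|---|---|---|
| 1 | 3.3 | 11.9% | 77.4% | 95.3% | 4.8% | 5.0–6.2% |
| 2 | 6.7 | 12.3% | 76.2% | 94.8% | 4.7% | 5.0–7.3% |
| 3 | 10.0 | 12.8% | 75.0% | 94.2% | 4.5% | 5.0–8.5% |

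For k = 3 and r = 40%: observed 27 × 0.05/30 = 4.5%, full (1.35 + 1.20)/30 = 8.5%, ratio 53%. For k = 1 and r = 5% the ratio is 97%.

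The upper limits show lost precision only, because they treat the withdrawn as similar to the rest. The last two columns show the bias if they are not. The risks of 5% and 5–40% are illustrations and do not come from the documents.

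**The case against.** The case on the other side is substantial, and much of it stands.

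- **The withdrawn are not all event-free.** A reader might infer that someone withdrawn for a serious AE sits in the denominator as a non-case. That person is already an SAE case, and an intolerable AE that led to a medical visit already counts as an MAAE. Later events in the same category do not change the percentage.
- **Withdrawal does more than end observation.** It also stops study procedures, including blood collection of up to 150 mL per visit and about 800 mL overall (Section 6), which can matter after a laboratory change or illness. Some listed reasons also apply before dosing.
- **Some follow-up survives.** Open AEs are followed to resolution or stability (6.1.1.4). Significant laboratory values are repeated (6.1.2). Pregnancies are followed to outcome after discontinuation (6.2). Related SAEs that the investigator learns of are reportable. The early termination visit itself collects AEs.
- **Attrition would be seen.** Rule 1c halts the cohort and higher-dose cohorts after one withdrawal following a Grade 3 AE. SAP 5.1 summarizes discontinuation and visit completion.
- **Boosters.** A reader might see a conflict between 4.2, which informs participants about available boosters so that they can choose whether to continue, and 5.8.2, which allows a booster after Day 29. Both can be true, and footnote k of Table 13-1 stops only the immunogenicity draws of boosted participants.
- **Higher risk.** Nothing shows that those withdrawn for noncompliance or ineligibility are more likely to have later events. For AE, laboratory and illness withdrawals it is plausible but not quantified.

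The study is also descriptive and open-label, the list is permissive, and the retention sentence precedes it. None of this restores scheduled collection of new events: following an open AE does not look for a new one, rule 1c pauses dosing but does not resume observation, and the retention sentence does not say what happens to someone who is withdrawn anyway.

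**Conclusion.** The gap is real but narrow. After the only dose, Section 4.2 permits investigator- or sponsor-initiated withdrawal, and no passage then keeps the participant under scheduled collection of new SAEs, MAAEs and AESIs to Day 180. The possible undercount is confined to event categories and preferred terms not already recorded in that participant.

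Its size cannot be fixed from the documents. For 1 to 3 withdrawals in a dose group of 30, an affected percentage is uncertain by at most 3.3 to 10 points. The loss of precision alone is small: with no events and 3 withdrawn, the upper limit moves from 11.6% to 12.8%. A larger bias needs both several withdrawals and a clearly higher later risk in those people, and neither is documented. The sample size figures in Section 7.2 reproduce and are not in question. This is an inexpensive improvement to the primary endpoint and does not invalidate the design.

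**What to change.** In Section 4.2, separate withdrawal before vaccination from withdrawal after it. For a vaccinated participant who meets a listed reason, state that blood draws and other study procedures may stop at the investigator's discretion, but that SAE, MAAE and AESI follow-up continues by telephone or televisit to Day 180. The exceptions are withdrawal of consent for follow-up, loss of contact, death, and termination of the study or site. The participant's right to leave is unchanged. Footnote k of Table 13-1 is a precedent.

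Add a CRF option for procedures stopped with safety follow-up continuing. Extend the televisit text in Sections 3.2 and 6 and in the note to Table 13-1, which now reserves televisits for a public health emergency or extenuating circumstance.

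The cost is the wording, one CRF option and a few extra remote contacts. The change also limits what an investigator or sponsor may stop after vaccination to procedures, leaving safety observation in place; this should be said openly. SAP Section 12 says the study was closed early. If follow-up is already over, the remaining action is to report follow-up time and withdrawals with reasons by dose group alongside the Day 180 percentages.
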